9.1 Extent of Exposure

Exposure to the study intervention for the Safety Population during the double-blind Study Intervention Period will be summarized for study intervention duration, calculated as the number of days from the date of the first dose of study intervention to the date of the last dose of study intervention, inclusive. Descriptive statistics (number of participants, mean, SD, median, minimum, and maximum) will be presented by study intervention group.

Patient-years, defined as exposure to the study intervention in years, will be summarized by study intervention for the Safety Population.

9.2 Measurement of Treatment Compliance

Dosing compliance for the double-blind Intervention Period is defined as number of capsules actually taken by a participant during that period divided by the number of capsules prescribed for that period multiplied by 100. This information will be obtained from the study intervention record of the participant's eCRF.

The number of capsules expected to be taken for the double-blind Intervention Period will be calculated by multiplying the number of days in that period by the number of capsules to be taken per day. Descriptive statistics for treatment compliance will be presented by study intervention group between 2 consecutive visits, as well as for the whole double-blind Intervention Period for the Safety Population.

9.3 eDiary Compliance

Participants will complete the electronic diary (eDiary) twice daily, once in the morning and once in the evening. Participant's eDiary compliance will be assessed based on the number of days with fully completed morning and evening assessments in a specific period. Morning or evening assessments will be considered fully completed if the participant responded to each question in the corresponding eDiary. eDiary compliance will be summarized for the Preintervention Period, double-blind Intervention Period, Postintervention Period, and for each week within each period based on the mITT Population.

Compliance for each participant/interval will be calculated using the following formula:

$$\% \text{Compliance} = \frac{100 * \# \text{ of days with completed morning and evening assessments within the interval}}{\# \text{ of expected days within the interval}}$$

On randomization day, the morning diary and/or clinic diary will be included in Preintervention Period and the evening diary will be included in the double-blind Intervention Period. On the day after last dose date, the morning diary will be included in the double-blind Intervention Period and the evening diary will be included in the Postintervention Period.

10 Efficacy Analyses

The efficacy analyses will be based on the mITT Population. All efficacy assessments will be determined by responses entered in the eDiary (morning eDiary, evening eDiary, or weekly eDiary) and eCRF (as appropriate).

Baseline values for efficacy endpoints related to daily eDiary responses will be derived from the eDiary in the Preintervention Period, specifically the time period from 14 days before randomization up to the time of randomization.

An SBM is a BM that occurs in the absence of laxative, suppository, or enema use on the calendar day of the BM or the calendar day before the BM. A complete spontaneous bowel movement (CSBM) is an SBM that is associated with a sense of complete evacuation.

The baseline SBM and CSBM weekly rates, stool consistency, straining, and abdominal symptoms (abdominal pain and bloating) will be derived as discussed in Section 16.3.5 from 14 days prior to randomization and up to randomization (as appropriate). A participant's baseline stool consistency and straining cannot be assessed if the participant does not have at least 1 SBM during the Preintervention Period. For participants who report no SBMs during a study period, the stool consistency and straining assessments will be considered missing for that study period in the analyses. Participants with missing baseline stool consistency and straining will be excluded from the respective stool consistency and straining analyses that involve change from baseline.

Baseline values for the participant-completed global change and severity items, and observer completed global change and severity items, will be based on the last non-missing assessment on or before the date of first dose of study intervention.

An observed cases (OC) approach to missing postbaseline data will be applied. Efficacy responses following onset of dose de-escalation will not be included for primary analyses. Supplemental summaries will be provided for primary and secondary endpoints by study intervention dose sequence incorporating the responses following the onset of dose de-escalation. No statistical testing will be performed to compare linaclotide doses. No multiplicity adjustment will be applied in this study for IBS-C participants.

10.1 Primary Efficacy Endpoint

The primary efficacy endpoint for IBS-C pediatric participants is 6/12 weeks APS (abdominal pain and SBM) + 2 responder. A 6/12 weeks APS + 2 responder is a participant that meets the

weekly APS + 2 responder criteria for at least 6 out of the 12 weeks of the intervention period. A weekly APS +2 responder is a participant who has an increase of at least 2 in the SBM weekly rate from baseline, AND a decrease of at least 30% in the mean abdominal pain score (combination daytime and nighttime) from baseline, during that study intervention week. Details on the derivations of SBM rate and abdominal pain score are provided in Section 16.3.4 and Section 16.3.5, respectively.

10.1.1 Main Analysis Approach

The primary efficacy endpoint will be summarized by counts and percentages by study intervention group for the mITT population.

Based on the review that the IBS-C disorder and the patient response to linaclotide treatment being similar between the adult and pediatric subjects, the primary statistical analysis is comprised of a partial extrapolation approach utilizing a Bayesian method. Following this approach, information is borrowed from the adult IBS-C population in Phase 2b study MCP-103-202 and Phase 3 registration studies LIN-MD-31 and MCP-103-302 (Carlin and Louis 2009). To enable this approach, the proposed IBS-C pediatric portion of study LIN-MD-64 will utilize the primary efficacy endpoint, 6/12 weeks APS + 2 responder to align with the adult registration studies where APC (abdominal pain and complete SBM) +1 responder is one of the primary efficacy endpoints.

The assumptions and details of the proposed Bayesian analysis are discussed below.

1. META-ANALYSIS of PLACEBO EFFECT in ADULTS: Utilizing the three adult studies, MCP-103-202, MCP-103-302, and LIN-MD-31, a meta-analysis was conducted to obtain an estimate for adult placebo effect related to 6/12 weeks APS + 2 responder rate. The estimated 6/12 Weeks APS + 2 responder rate for placebo was 0.16 and upper bound of 95% confidence interval (CI) of the placebo responder rate was 0.18.
2. PRIOR for LINACLOTIDE TREATMENT: Utilizing the three adult studies, MCP-103-202, MCP-103-302, and LIN-MD-31, a meta-analysis of the adult studies was conducted to obtain an adult prior distribution for linaclotide 290 ug responder rate. All subjects administered 266 ug to 300 ug in these contributing studies were included and considered for linaclotide 290 ug. Since this responder rate is bounded between [0,1], the prior distribution of linaclotide responder rate (θ) can be approximated by the Beta distribution. In this case, α (aggregate number of adult responders) and β (aggregate number of adult non-responders)

$$\theta \sim \text{Beta}(\alpha, \beta),$$

where $\alpha = 340$ and $\beta = 550$ based on meta-analysis of 3 adult contributing studies (MCP-103-202, LIN-MD-31 and MCP-103-302).

In this Bayesian analysis, this distribution forms the prior for the pediatric responder rate in linaclotide treated subjects for each linaclotide arm (145 ug and 290 ug).

3. LIKELIHOOD FUNCTION: Let N be the sample size of IBS-C participants in LIN-MD-64 and for each $\theta = \Pr(\text{Pediatric subject is a responder})$, let X be the observed number of pediatric patients who are responders in LIN-MD-64. Then, given θ , X will have a binomial likelihood function, which can also be simply expressed as follows:

$$X | \theta \sim \text{Binomial}(N, \theta)$$

4. DOWNWEIGHT PRIOR: Due to the large number of adult subjects, a down weighting factor, w , bounded $(0,1)$, is prespecified, such that the prior in step 2 becomes $\theta \sim \text{Beta}(w*\alpha, w*\beta)$

Down-weighting in this manner will allow each adult patient to be 'worth' the fraction w of a new pediatric patient. An alternative way of expressing this 'worth' and describing the impact of the weights would be to describe an effective sample size (ESS). ESS is calculated as $(\alpha + \beta)*w$ and is interpreted as the amount of new samples that the adult data will be equivalent to in an analysis.

5. POSTERIOR for TREATMENT EFFECT: The posterior distribution for linaclotide responder rate utilizing IBS-C pediatrics data in Step 3 is also a Beta distribution with down-weighted prior in Step 4:

$$\theta | X \sim \text{Beta}(X + w*\alpha, N - X + w*\beta)$$

6. For each linaclotide dose arm, calculate the Bayesian probabilities (Bayesian powers) of the pediatric posterior (i.e., pediatric responder rate based on pediatric posterior distribution in Step 5) in two ways as below:
 - (a) demonstrating superiority to the adult placebo effect, based on the 2.5 percentile of the posterior distribution exceeding the upper bound 0.18 of 95% CI of the adult placebo effect calculated in Step 1
 - (b) demonstrating superiority to the adult placebo effect, based on the 2.5 percentile of the posterior distribution exceeding the adult pooled placebo estimate of 0.16 as calculated in Step 1.

7. Repeat Steps 4 to 6 for a range of values of “w” ; plot Bayesian probability as function of “w” as specified in Step 6. Range of w is prespecified as (0.0067, 0.0200), corresponding to an ESS for adult data providing the informational equivalent of approximately 6 to 20 pediatric subjects.

10.1.2 Supplemental Analysis

The following supplemental and sensitivity analyses on the primary endpoint will be performed:

- The primary efficacy endpoint will be summarized by counts and percentages and 95% Exact binomial CI by study intervention group for the mITT population.
- The proportion of responders will be compared to 0.18 (the upper bound of the 95% CI of the adult placebo rate from the meta-analysis) based on a one-sample proportion exact test, and the corresponding p-value will be provided for the pooled linaclotide dose groups and for each individual linaclotide dose group.
- Bayesian probabilities of the pediatric posterior in Step 6 (Section 10.1.1) will also be calculated with a non-informative prior (i.e., Beta(1, 1)) for linaclotide treatment.
- The primary efficacy endpoint will also be summarized by counts and percentages by study intervention incorporating all efficacy responses including the responses following onset of dose-de-escalation.

Weekly responder rates (counts and percentages) will be provided for APS+2 responders by study intervention group. The 95% Exact binomial CI for weekly responder rate at week 12 will be presented.

Additional Sensitivity Analyses with Different Missing Data Handling Methods

For any postbaseline analysis week, if participant has less than 4 completed diary days (i.e., completed both morning and evening diaries) in an analysis week, participant's corresponding week's analysis value for SBM or abdominal pain (AP) combination score will be considered missing and the postbaseline missing week during the intervention period will be imputed as follows.

- Missing weekly SBM or AP combination scores will be imputed using multiple imputation (MI) assuming missing at random. Subjects with missing weekly values will be characterized as responders or non-responders based on the derived weekly SBM or AP combination scores from MI datasets. The imputed endpoints will be analyzed using each of the 30 datasets. SAS PROC MIANALYZE will be used to generate the final percentages and 95% CI for the responder rate based on normal approximation using Rubin's rule.

The following tipping-point analysis will be performed assuming missing-not-at-random as another sensitivity analysis to evaluate the impact of missingness assumption for the analysis result.

- The achievement of the primary efficacy endpoint requires a participant to meet the weekly APS + 2 responder criteria for at least 6 out of the 12 weeks of the intervention period. For participants with missing data on weekly SBM or AP combination scores, the missingness may or may not affect the responder status in the primary endpoint. For example, if a participant already met the weekly APS + 2 responder criteria for 6 weeks and had missing data for 3 weeks, the participant would achieve the primary endpoint, regardless of the missing data. On the other hand, if a participant met the weekly APS + 2 responder criteria for 2 weeks, did not meet the weekly APS + 2 responder criteria for 7 weeks, and had missing data for the other 3 weeks, the participant would not achieve the primary endpoint, regardless of the missing data. In this analysis, the participants with missing data that potentially impacts the responder status will be sequentially imputed as responders (i.e., from 0 to the total number of participants with missing data that potentially impacts the responder status) and the series of 95% Exact binomial CI will be presented.

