10.1.3 Estimand Framework

Population

The target population is participants with IBS-C, ages 7-17 years old, satisfying the inclusion and exclusion criteria as specified in Sections 5.1 and 5.2 of the protocol (Version June-2020), respectively.

The analysis population is mITT as discussed in Section 6.3.

Variable

The variable is the primary efficacy endpoint defined in Section 10.1, which is 6/12 weeks APS (abdominal pain and SBM) + 2 responder as derived from twice daily responses in eDiary (morning and evening). SBM is derived based on responses for BM and rescue medication in the eDiary twice daily (morning and evening). Abdominal pain score is also derived based on responses in the eDiary twice daily for abdominal pain.

Accounting for Intercurrent Events in the Primary Efficacy Analyses

The following intercurrent events are considered for the primary efficacy analyses. All the intercurrent events are handled based on the composite strategy.

- The BMs for the participants who took a laxative, enema, or suppository on the calendar day of the BM or the calendar day before the BM will not be considered as SBMs for the analysis.
- Participants who discontinue prematurely during but prior to the completion of the double-blind Study Intervention Period will have their eDiary data included up to the morning diary following the last dose date for primary endpoint. The early discontinued participants will be considered non-responders for the following weeks for primary endpoint.
- eDiary responses following the onset of dose de-escalation will not be included. The participants with dose de-escalation will be considered non-responders for the subsequent study intervention weeks (after the onset of dose de-escalation) for the primary endpoint based on the randomized study intervention group.
- A participant has to have at least 4 completed diary days per study intervention week to be considered a responder for that week and otherwise, the participant will be considered non-responder for that week. A completed diary day is a day in which both morning and evening eDiary entries are filled out by a study participant.

Population-level Summary

The population-level summary for the primary endpoint is the proportion of participants satisfying the APS + 2 responder criteria for at least 6 out of 12 weeks during the study intervention period for each linaclotide dose.

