withdrawn participant's Intervention Period and all subsequent Intervention Period weeks will be missing for that participant.

Table 16-3 below presents the weekly periods assigned for the efficacy analysis of the participant weekly diary data related to global severity items and global change items.

Table 16-3. Analysis Time Windows for Efficacy Analysis - Weekly Questions

Analysis Week	Begins ^a	Ends ^a
Week -2	Visit 2 day	Visit 2 day + 7
Week -1 (Baseline)	Visit 2 day + 8	Day 1
Week 1	Day 2	Day 8
Week 2	Day 9	Day 15
Week 3	Day 16	Day 22
Week 4	Day 23	Day 29
Week 5	Day 30	Day 36
Week 6	Day 37	Day 43
Week 7	Day 44	Day 50
Week 8	Day 51	Day 57
Week 9	Day 58	Day 64
Week 10	Day 65	Day 71
Week 11	Day 72	Day 78
Week 12	Day 79	last dose date +1
Post-intervention	Day of last dose date + 8	Day of end of study visit

- a. Begin and end of each week from Week 1 onwards are relative to the date of the first dose of double blind study intervention. Day 1 = the date of the first dose of double blind study intervention. There is no Day 0 or Week 0. End of Week 1 to Week 12 will be day of last dose + 1 or corresponding end day in table whichever comes earlier.

Participants who rollover to the long-term safety study, LIN-MD-66, before the EOS visit (i.e. Visit 8, post-intervention visit) are not required to have the EOS visit or post-intervention visit.

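### The IBS-C multiple-imputation sensitivity analysis can turn weeks after early discontinuation into response, so it does not test the composite estimand

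*SAP*

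**What the plan says.** **Estimand (IBS-C SAP 10.1.3).** For the primary efficacy analyses, "All the intercurrent events are handled based on the composite strategy". On stopping early: "The early discontinued participants will be considered non-responders for the following weeks for primary endpoint". Diary data count only up to the morning diary after the last dose. Weeks after onset of dose de-escalation are also non-response. For a week with fewer than 4 completed diary days, "otherwise, the participant will be considered non-responder for that week". Protocol 9.2.2 sets out the same rules.

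**Sensitivity analyses (IBS-C SAP 10.1.2).** Two analyses stand under a subheading that calls them additional sensitivity analyses. The trigger is "For any postbaseline analysis week, if participant has less than 4 completed diary days". That week's SBM or pain value becomes missing, and "the postbaseline missing week during the intervention period will be imputed as follows". The method is then given: "Missing weekly SBM or AP combination scores will be imputed using multiple imputation (MI) assuming missing at random". There are 30 datasets, and weeks are scored as response or not from the imputed values. The tipping-point analysis, presented as missing-not-at-random, works at participant level: "the participants with missing data that potentially impacts the responder status will be sequentially imputed as responders", from none of them up to all.

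**Data windows (IBS-C SAP 16.2).** When a participant withdraws, the current week is cut short and "all subsequent Intervention Period weeks will be missing for that participant".

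**The concern.** Under a composite strategy the outcome of a week after discontinuation is known: it is a failure by definition. It is not a missing value. An analysis that imputes that week asks what would have happened had the child continued, which is a hypothetical question. If its result agrees with the main analysis, a reader of the study report will take this as evidence that the composite result is robust to missing data, and it is not that evidence.

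The exposure can be wide. The mITT population in IBS-C SAP 6.3 requires only one dose, so a child who stops after Day 1 would have all 12 weeks imputed. The text suggests an oversight rather than a choice. Section 17 says these analyses were added to handle missing data and announces no new estimand. The FC SAP, in 10.1.4.4, states for its worst-response analysis that early discontinuers are treated as in the main analysis. The IBS-C SAP has no such sentence.

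**Working it through.** **Step 1. Follow each kind of week through the text.**

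| Week | Main analysis (10.1.3) | MI (10.1.2) | Tipping point (10.1.2) |
|---|---|---|---|
| On treatment, 4 or more completed days | scored from data | scored from data | scored from data |
| On treatment, fewer than 4 | non-response | imputed | participant set to responder for k > 0 if the week could matter |
| After last dose | non-response | no included diary days, so the trigger is met; 16.2 calls it missing; imputed | as above |
| After de-escalation, diary still kept | non-response | trigger not met by de-escalation itself; text silent | text silent |

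Here k is the number of participants set to responder. The conflict in question is the third row.

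**Step 2. One participant.** A child responds in 4 of 5 weeks and then stops. Under the composite rule the count is 4 of 12, below 6, so the child is a non-responder. Under MI the child needs at least 2 of the 7 remaining weeks. With imputed weekly probability q,

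P(responder) = 1 − (1 − q)^7 − 7q(1 − q)^6.

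- q = 0.3: 1 − 0.082 − 0.247 = 0.67
- q = 0.5: 1 − 0.008 − 0.055 = 0.94
- q = 0.8: above 0.99

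Not every stopper changes status. A child with 6 response weeks before stopping is a responder under both rules. A child with 1 response in 9 weeks can reach at most 1 + 3 = 4 and is a non-responder under both.

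**Step 3. The plan's own figures.** The plan gives no figure for the effect of MI. The nearest figures are the Bayesian powers in Tables 14-1 and 14-2. With w = 0.017 the prior is Beta(340 × 0.017, 550 × 0.017) = Beta(5.78, 9.35). At N = 50, success requires the 2.5th percentile of Beta(X + 5.78, 50 − X + 9.35) to exceed the threshold. That needs X ≥ 12 for 0.16 and X ≥ 13 for 0.18. The exact beta-binomial powers are 0.860 and 0.822, against 0.854 and 0.809 stated. The stated values come from 1000 simulated trials (standard error 0.011 to 0.012), so they reproduce. X is the responder count of the main analysis, and the imputed rates do not enter it.

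**Step 4. Size across an arm.** The documents give neither a discontinuation rate nor a weekly response rate, so both are assumed.

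- Each participant's weekly response probability is Beta(1.5m, 1.5(1 − m)), with mean m.
- A fraction d stops, with the last on-treatment week uniform on 1 to 11 and independent of response.
- Composite: responder if the observed response weeks y ≥ 6.
- MI under MAR: draw p from Beta(1.5m + y, 1.5(1 − m) + L − y), where L is the number of observed weeks. Draw the other 12 − L weeks as Binomial(12 − L, p) and apply the 6-week rule.

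This imputes weekly response directly rather than SBM and pain scores, and has no on-treatment gaps. Results at m = 0.35, from 400,000 simulated participants per row, with gaps taken before rounding:

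| Discontinuation d | Composite | MI | Gap (points) | Gap for m = 0.25 to 0.45 | Top of tipping-point range |
|---|---|---|---|---|---|
| 5% | 0.337 | 0.348 | 1.1 | 0.8 to 1.5 | 0.370 |
| 10% | 0.326 | 0.349 | 2.3 | 1.6 to 3.0 | 0.392 |
| 20% | 0.302 | 0.347 | 4.6 | 3.2 to 6.0 | 0.434 |
| 30% | 0.280 | 0.349 | 6.9 | 4.7 to 9.1 | 0.478 |

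The MI column is flat because it restores the rate that would hold had nobody stopped. At 20% discontinuation the gap is 0.032 × 50 = 1.6 to 0.060 × 50 = 3.0 extra responders per 50.

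**The case against.** **The section is titled Supplemental Analysis**, the composite rules sit under a heading limited to the primary efficacy analyses, and a supplementary analysis may target another estimand. This stands in part: the calculation is legitimate if it is presented that way. But the subheading calls both analyses sensitivity analyses, and no other estimand is stated.

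**The scope is inferred.** No sentence says outright that weeks after discontinuation are imputed. Section 16.2 also speaks of the end of the withdrawn participant's own Intervention Period, so later weeks could be read as falling outside it. But the same sentence calls those later weeks Intervention Period weeks that are missing, and 10.1.2 covers any postbaseline week. The literal reading includes them, and the ambiguity itself needs removing.

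**Imputation can only raise the rate, but that is not specific to this flaw.** The main analysis already scores every short week as failure, and 10.1.3 lists the diary-day rule under the same composite strategy. Imputing on-treatment gaps therefore also moves the rate upward. This stands. What sets the weeks after last dose apart is that treatment has stopped, not the direction of the change.

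**The tipping-point series starts at k = 0**, which is the composite result, and shows its whole range. This stands, so the point is strongest for the MI analysis.

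A reader might go further in three ways that the documents do not support:

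- That weeks after de-escalation are certainly imputed. A de-escalated child stays on study and keeps filling in the diary, so de-escalation alone does not meet the trigger. Section 10.1.2 also has a separate summary using those responses. The text is unclear, no more.
- That the success bar moves. MI yields percentages with a 95% CI, and the tipping point yields exact CIs. Neither feeds the comparison with 0.16 or 0.18.
- That each early stopper gains the adult response rate, 340/890 = 0.38, so that 5 of 50 stopping adds 1.9 responders, or 3.8 points. This ignores the weeks observed before stopping. The simulated gap at 10% is 2.3 points.

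**Conclusion.** The point holds for weeks after early discontinuation. As written, the MI analysis replaces outcomes that the estimand fixes as failures with imputed values that may be response, so it cannot serve as a sensitivity analysis of the composite estimand. The same applies to the tipping-point series for k > 0. At an assumed mean weekly response of 0.35, the size is about 1 point at 5% discontinuation, rising to 6.9 at 30%. These figures rest on assumed discontinuation and response rates, with stopping unrelated to response. The mechanism does not depend on them. The primary result and the Bayesian criterion are untouched. The harm is confined to how robustness would be read.

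**What to change.** In IBS-C SAP 10.1.2:

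- Keep weeks after the last dose as non-response in every imputed dataset and in the tipping-point count. Impute only on-treatment weeks with fewer than 4 completed diary days.
- State explicitly whether weeks after onset of de-escalation follow the same non-response rule in these two analyses.
- If the sponsor wants to keep the imputation of weeks after discontinuation, label it supplementary and state its hypothetical estimand.

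The cost is SAP wording, one flag in the imputation program, and a slightly less favourable sensitivity figure.
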